6.2.3. Investigational Product Administration

During the double-masked period, the unmasked investigator will perform all IP administrations (DE-109 440 μ g, Sham, and Dummy [an undisclosed, fixed dose of DE-109 in the range of 44 μ g to 880 μ g]).

The procedures for IP administration to a single study eye are shown in Table 6. Note that the subjects' pupils will already have been dilated by the masked investigator/staff prior to the conduct of the pre IP administration assessments. Detailed guidance regarding IP administration, including administration to both eyes, is provided in the Investigational Product Manual.

Notes	DE-109 440 μg and Dummy (an undisclosed, fixed DE-109 dose in the range of 44 μg to 880 μg)	Sham
	sked investigator or designee should ensure that the n. The use of sterile gloves and face mask by the un	
	1. Administer at least 1 drop of topical anesthetic (topical 0.5% proparacaine hydrochloride ophthalmic solution or an equivalent topical ophthalmic anesthetic is recommended. Adjunctive administration of subconjunctival anesthesia is permitted at the discretion of the unmasked Investigator.	Same as DE-109
	2. Administer 5% povidone iodine to the study eye.	Same as DE-109
	3. Use a sterile cotton-tipped applicator to remove excess fluid from the lower conjunctival sac.	Same as DE-109
Step #4 may be omitted per the unmasked investigator's discretion.	4. Take 2 sterile cotton tipped applicators and thoroughly soak with 0.5% proparacaine topical anesthetic eye drops or an equivalent topical ophthalmic anesthetic. Place the soaked applicators, side by side, gently but firmly on the conjunctival surface at the area of the entry site described below in Step 10 and hold in place for approximately 1 minute.	Same as DE-109
	5. Insert sterile eyelid speculum.	Same as DE-109
	6. Place sterile eye drape over study eye.	Same as DE-109
	 Prior to starting the injection procedure, DE-109 should have been prepared as described in Section 6.2.2, with the appropriate dose of IP drawn into a 250 μL single-use plastic syringe. ENSURE THAT THERE ARE NO AIR BUBBLES IN THE SYRINGE OR NEEDLE HUB. 	Removal and thawing procedures are the same for Sham as for DE-109 (Section 6.2.2). A syringe loading procedure similar to DE-109 should be performed; no drug product will be drawn up into the syringe.

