3.2. Randomization and Masking

For the double-masked period, eligible subjects (total sample size of approximately 200 subjects) will be randomized in a 2:2:1 ratio to the DE-109 440 μ g arm (80 subjects), the Sham arm (80 subjects), and the Dummy arm (40 subjects). The randomization will be stratified by baseline systemic (oral) corticosteroid use (yes/no), number of subject's enrolled eyes (1 eye/2 eyes), and region (US/non-US). A separate permuted-block randomization with a fixed block size will be generated for each stratum. A computer algorithm for random number generation will be used to generate the randomization and an IWRS will be used to administer the randomized assignment of subject eyes to treatment arms. Subjects with both eyes enrolled will be assigned to the same treatment arm in both eyes.

The 6-month, comparative period of the study is double-masked and sham-controlled. The sham procedure mimics an intravitreal injection (the blunt end of an empty syringe is pressed against an anesthetized eye). To retain the masking of the investigator, a separate, unmasked investigator will be responsible for administering the IP (DE-109 intravitreal injections and sham). The masked investigator will conduct assessments prior to IP administration; the unmasked investigator will administer the IP and conduct the post-administration assessments. Thus, the treatment assignments will be masked to Santen (except Clinical Supply and Quality Assurance personnel, as required), study subjects, and masked investigators.

The dummy arm is included in the double-masked period of the study to help ensure masking of treatment assignment given the use of a sham control. All subjects randomized to the dummy arm receive intravitreal injections of DE-109 every 2 months at an undisclosed fixed dose of 44µg to 880µg (doses of DE-109 in this range have previously been shown to have an acceptable safety profile). The dose in this arm will not vary between participating sites or subjects randomized to this arm. Except for a limited number of Santen employees in Clinical Supply and Quality Assurance as required, the dose of DE-109 in the dummy arm will remain undisclosed to investigators, CROs, and Santen employees involved in the study conduct.

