3.3. Sample Size Planning

Assuming a 30% VH 0 response rate for DE-109 440 μ g group and a 12% response rate for the sham treatment group, 160 subjects (80 subjects per arm) is required to achieve 80% power to detect such a difference in response rate between the DE-109 440 μ g group and the sham treatment group using the Pearson's Chi-square test (two-sided, $\alpha = 0.05$). Including approximately 40 subjects in the dummy arm, a total of approximately 200 subjects with active NIU-PS will be randomized in a 2:2:1 ratio to DE-109 440 μ g, sham, and dummy arms. Because some subjects will contribute two study eyes to this study, the planned sample size of 80 subjects

in both the test (DE-109 440 $\mu g)$ and control (sham procedure) arms will achieve more than 80% power.

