8. EFFICACY ANALYSES

8.1. Efficacy-Related Definitions

8.1.1. Study Eye and Fellow Eye

The *study eye* of a treated subject will be the eye that received an investigational product (IP) at baseline (Day 1). For subjects who enrolled both eyes in the study and both eyes received IPs at baseline (Day 1), both of their eyes will be considered as study eyes. Number of enrolled study eyes for each subject is defined as the number of eyes that received an IP administration at baseline (Day 1).

For subjects who enrolled one eye in the study, the other eye which did not receive an IP at baseline (Day 1) will be the non-study eye, or *fellow eye*. In a case when a subject enrolled in the study with both eyes eligible but only one of his/her eyes received an IP during the Double-Masked period, the eye which received an IP will be considered study eye, the eye which did not received any IPs will be considered fellow eye.

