8.2.1. Primary Analyses

The primary efficacy endpoint, VH 0 response, is defined as having a VH score of 0 at Month 5 (modified SUN scale). For the primary endpoint, the VH 0 response rate will be evaluated in accordance with the following null (versus alternative) hypothesis:

$$H_0: \pi_{sham} = \pi_{440}$$
versus

$$H_A: \pi_{sham} \neq \pi_{440}$$

where π_{sham} and π_{440} denote the response rate for sham and 440 µg DE-109, respectively.

The Cochran-Mantel-Haenszel (CMH) test with Row Mean Scores statistic (Yu et al., 2020), stratified by pooled strata based on the number of enrolled eyes from a subject (one eye or two eyes), baseline systemic (oral) corticosteroid use (yes or no), and region (US or non-US). Such pooling is needed to avoid the situation where subjects in too small strata might all have the same responses (either success or failure); hence, do not contribute to the test. To guarantee that

a pooled stratum has at least one success and one failure, the pooling algorithm will be performed as follows:

- Determine the number of subjects in each stratum, defined by crossing the number of enrolled eyes, baseline systemic corticosteroid use, and region.
- Within each combination of number of enrolled eyes and region, if one or both strata, stratified by corticosteroid use, have less than 25 subjects, then those strata will be pooled.
- Within each stratification factor level based on number of enrolled eyes, if at least one of (pooled/unpooled) strata have less than 25 subjects, then those strata will be pooled together.

The pooling algorithm will be performed based on the available data prior to the unmasking of the randomization. At the interim analysis, only number of enrolled eyes will be used as the stratification factor.

Study eyes will be treated as non-responders if they meet at least one of the following criteria:

- 1. A study eye is rescued due to the protocol-specified worsening of uveitis (Section 8.1.6)
- 2. A subject discontinued from the study due to lack of efficacy or adverse events
- 3. A study eye meets the protocol-specified worsening of uveitis rescue criteria (Section 8.1.6) regardless whether the eye received any rescue therapies

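### SAP 8.1.1 counts enrolled eyes by Day 1 dosing, so the primary and interim CMH strata need not be the randomised ones; its two paragraphs also leave an eye first dosed at Month 2 unclassified

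*SAP*

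**What the plan says.** SAP 3.2, like protocol 6.3, fixes three strata at randomisation: whether the subject takes oral corticosteroids at baseline, whether one or two eyes are enrolled, and whether the site is in the US. Protocol section 5 lets the investigator decide whether to enrol both eyes once eligibility is confirmed. Under protocol 8.1.3 the eyes are then randomised through the IWRS, and only after that is product prepared and given. Protocol 6.2.3 says who gives it: "During the double-masked period, the unmasked investigator will perform all IP administrations".

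SAP 8.2.1 runs the primary CMH test "stratified by pooled strata based on the number of enrolled eyes from a subject (one eye or two eyes"), together with baseline oral corticosteroid use and region. Its pooling steps merge corticosteroid strata and then regions, always within a level of number of eyes. At the interim (SAP 5.5.1 and 8.2.1) number of eyes is the only stratum.

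SAP 8.1.1 defines the count: "Number of enrolled study eyes for each subject is defined as the number of eyes that received an IP administration at baseline (Day 1"). Its second paragraph takes the double-masked period as its window, for a subject enrolled with both eyes eligible but dosed in one only: "the eye which received an IP will be considered study eye, the eye which did not received any IPs will be considered fellow eye". SAP 8.2 does not use fellow-eye data for efficacy. The FAS (protocol 9.4, SAP 6.2) and the primary estimand (protocol 9.1) cover eyes with at least one administration.

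**The concern.** A stratification factor should keep the value it had when the subject was randomised. Here a factor known before assignment is given a definition that depends on what happened after it, at the hands of someone who knows whether a needle or a sham is due. For most subjects the two values agree. They differ for a two-eye subject with an eye not dosed on Day 1, who moves to the one-eye stratum.

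The factor enters the interim, primary, key secondary and binary secondary CMH tests and the VFQ-25 ANCOVA. Stratum counts also drive the 25-subject pooling thresholds. Separately, the definitions of study eye and fellow eye do not cover every case, so two programmers could build different primary datasets from the same text.

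**Working it through.** **Definitions, case by case (IWRS count against SAP 8.1.1 count)**
- One eye randomised and dosed on Day 1: 1 and 1.
- Two eyes randomised, both dosed on Day 1: 2 and 2.
- Two eyes randomised, one never dosed in the double-masked period: 2 and 1. The undosed eye is a fellow eye by paragraph two. It would be outside the FAS in any case.
- Two eyes randomised, one first dosed at Month 2: 2 and 1. The late eye is not a study eye by paragraph one, which looks at Day 1. It is not a fellow eye by paragraph two, because both eyes received product in the double-masked period. Yet it was randomised and had an administration, which is what the FAS asks.

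**The plan's own figure.** SAP 3.3 gives "Assuming a 30% VH 0 response rate" for DE-109 440 µg "and a 12% response rate for the sham treatment group", and says "160 subjects (80 subjects per arm) is required to achieve 80% power". With pooled rate 0.21 and two-sided alpha 0.05:

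n = {[1.960 × √(2 × 0.21 × 0.79) + 0.842 × √(0.30 × 0.70 + 0.12 × 0.88)] / 0.18}² = 79.2, so 80 per arm, with power 0.804. The figure reproduces. The formula has no strata, so this point does not touch it.

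**Effect of moving stratum.** The documents give neither the share of two-eye subjects (s) nor the fraction of them with one eye undosed (d), so both are assumed. Take 80 per arm, no treatment effect, omission in the DE-109 arm only, one-eye response 15%, and two-eye response 5 or 10 points lower. With n2 = 80s, n1 = 80 − n2 and m = d × n2 subjects moved:
- One-eye stratum bias = m × (p2 − p1) / (n1 + m); Mantel-Haenszel weight = a × b / (a + b).
- Smallest case (s = 0.2, d = 0.05, gap 5): m = 0.8; bias = 0.8 × (−5) / 64.8 = −0.06 points; weights 32.2 and 7.8; overall −0.05.
- Middle case (s = 0.3, d = 0.1): m = 2.4; overall −0.15 (gap 5) or −0.29 (gap 10).
- Largest case (s = 0.5, d = 0.2, gap 10): m = 8; bias = 8 × (−10) / 48 = −1.67; weights 21.8 and 17.8; overall −0.92.

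The sign is against DE-109. It would reverse if two-eye subjects responded better. In the largest case the mean rate is 10%, so the standard error is about √(2 × 0.10 × 0.90 / 80) = 4.7 points and the shift is 0.19 standard errors. Taken alone, that gives a two-sided rejection rate of about 0.039 + 0.016 = 0.054, with the excess on the side against DE-109.

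**Effect of losing the eye.** If the undosed eye would have responded e points less often than its partner, the DE-109 subject-mean rate rises by m × (e/2) / 80:
- s = 0.2, d = 0.05, e = 15: 0.8 × 7.5 / 80 = +0.08 points.
- s = 0.3, d = 0.1, e = 15: 2.4 × 7.5 / 80 = +0.23.
- s = 0.5, d = 0.2, e = 30: 8 × 15 / 80 = +1.5.

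Set roughly against the stratum shift, the largest case nets −0.92 + 1.5 = about +0.6, and the middle case is near zero.

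**Simulation.** A stratified row-mean-score CMH test was run on each subject's share of responding eyes: 80 per arm, assumed between-eye correlation 0.5, two-eye share 20% or 40%, and the same response rate for one- and two-eye subjects. There were 8,000 runs at 12% in both arms and 4,000 at 30% against 12%. The comparison is all randomised eyes kept in their randomised stratum against SAP 8.1.1.
- Type I error: 0.044 to 0.053 as randomised, 0.044 to 0.052 under 8.1.1 (simulation error about 0.0025).
- Eye omitted at random: the rate difference moves by at most about 0.03 points.
- Worse eye omitted, DE-109 arm only, in 10%, 25% or 50% of two-eye subjects: the null difference rises by 0.1–0.2, 0.2–0.4 or 0.5–0.9 points. At 30% against 12% it rises by 0.2–0.3, 0.5–0.8 or 1.0–1.8.
- Power moves by up to about 2 points at 25% omission and by −4 to +3 at 50%.
- No eye omitted: the two analyses are identical.

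**Outer bound**, if every omitted eye were a non-responder: with 96 eyes per arm and 1.6 omitted, 12% becomes 12 × 96 / 94.4 = 12.2%. With 112 eyes and 16 omitted, 12% becomes 14.0% and 30% becomes 35.0%.

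**The case against.** Four points can fairly be made for the plan.

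- **The link to the CMH test is inferred.** SAP 8.1.1 speaks of enrolled study eyes. SAP 8.2.1 speaks of enrolled eyes, close to the randomisation wording, and does not cite 8.1.1. Appendix C, which 8.2.1 cites for the code, is not in the copy available and might settle the matter. This stands as a limit: the primary test may be meant to use the randomised strata. But 8.1.1 holds the only definition of the count, and nothing available says that the strata come from the IWRS.
- **A reader might infer that 8.1.1 removes randomised eyes from the comparison.** The documents do not support that for eyes never dosed. The FAS and primary estimand already require an administration, and the amendment summary records that population as aligned with the estimands and acceptable to the regulator. Editing 8.1.1 would not bring those eyes back.
- **A reader might infer that omission depends on arm.** An unmasked injector makes it possible, but no omission rate is given for either arm. Reluctance to treat both eyes on one day is largely screened out, since the choice to enrol both comes before randomisation.
- **The CMH method cited for several anatomical regions cannot be inspected here.** Its handling of a subject who contributes one eye to the two-eye stratum must be confirmed when the rule is written.

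**Conclusion.** The point holds as a fault of specification. As written, the number-of-eyes factor takes its value from Day 1 dosing rather than from the randomisation record, and 8.1.1 leaves an eye first dosed at Month 2 unclassified.

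It is not a threat to alpha or power on anything the documents show. The effect is zero unless a randomised eye is missed on Day 1. Otherwise simulated type I error is unchanged and shifts are mostly under 1 point; they exceed it only at extreme assumed omission or response gaps. The simulated shifts also overstate what 8.1.1 adds, because the FAS alone would drop a never-dosed eye.

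It is tempting to add the stratum shift to the dropped-eye effect. With two-eye response assumed lower, they have opposite signs and offset. All sizes rest on assumed two-eye shares, omission rates, between-eye correlation and response gaps.

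**What to change.** - In SAP 8.1.1 and 8.2.1, define the number-of-eyes stratum as the IWRS value at randomisation. Use it in the interim, primary, key secondary and binary secondary CMH tests. A two-eye-stratum subject dosed in one eye contributes that eye.
- Reconcile the two paragraphs of 8.1.1: a study eye is an eye randomised as such, and FAS membership still requires at least one administration. An eye first dosed at Month 2 then has a clear place.
- Report by arm the randomised eyes not dosed on Day 1.
- Optional: a sensitivity analysis counting undosed randomised eyes as VH 0 non-responders. It lies outside the stated estimand.

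The cost is SAP wording and one count, settled before unmasking; the IWRS already holds the value. The one drawback is that a few subjects in the two-eye stratum may contribute a single eye. If no eye was missed, every result is the same.

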8.1.2. Baseline Score

For any measure, the *baseline score* is the last observed measurement prior to the first administration of the IP.

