Record the study visit in the EDC system (Medidata) for Month 3.

8.1.8. Double-Masked Treatment Period, Month 4

Allowable visit window: Day 120 ± 3 days; other procedures/details are the same as for Month 2 (Section 8.1.6).

8.1.9. Double-Masked Treatment Period, Month 5

Note: Subjects must fast 8 hours prior to the blood draw for hematology and chemistry laboratory tests taken at Month 5.

Allowable visit window: Day 150 ± 3 days

Visit details:

Perform the following assessments in both eyes:

- Perform physical examination. Note: if this was performed at Month 3 under a previous version of the protocol it does not need to be repeated.
- Record vital signs. Note: if this was performed at Month 3 under a previous version of the protocol it does **not** need to be repeated.

- Collect fasting blood for serum chemistry and hematology tests for laboratory analysis. Note: if these samples were collected at Month 3 under a previous version of the protocol they do **not** need to be repeated.
- Obtain urine sample for urinalysis. Note: if this sample was collected at Month 3 under a previous version of the protocol it does **not** need to be repeated.
- Assess BCVA using ETDRS charts.
- Administer dilation eye drops (1% Mydriacyl and 2.5% phenylephrine or equivalent applied topically).
- Administer the VFQ-25. Note: if this was performed at Month 3 under a previous version of the protocol it does **not** need to be repeated.
- Measure IOP.
- Perform slit-lamp biomicroscopy.
- Perform indirect ophthalmoscopy.
- Obtain fundus photography.
- Perform fluorescein angiography.
- Perform OCT.
- Assess for adverse events.
- Record concomitant medications (including systemic corticosteroid medication status).

Record the study visit in the EDC system (Medidata) for Month 5.

8.1.10. Double-Masked Treatment Period, Month 6

Allowable visit window: Day 180 ± 7 days; other procedures/details are the same as for Month 2

8.1.11. Open-Label Treatment Period, Month 7

Allowable visit window: Day 210 ± 7 days; other procedures/details are the same as for Month 1 (Section 8.1.5).

8.1.12. Open-Label Treatment Period, Month 8

Allowable visit window: Day 240 ± 7 days; other visit procedures/details are the same as for Month 2 (Section 8.1.6).

8.1.13. Open-Label Treatment Period, Month 9

Allowable visit window: Day 270 ± 7 days; other visit procedures/details are the same as for Month 1 (Section 8.1.5).

8.1.14. Open-Label Treatment Period, Month 10

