3.4. Visits and Assessments

The schedule of activities (SoA) is provided in Table 1.

	Screening		Double-Masked Period Visits					Open-Label Period Visits							
	Screening (Within 30 days prior to D1; i.e., D -30 to D -1)	E (Base	01 eline)	D14	M1	NN	12, 14	M3	M5	N	16 ^a	M7, M9, M11	N M	18, [10	M12/ Exit/ Early Termina- tion
Study day		E	01	D14	D30	D D	60, 120	D90	D150	D	0180	D210, D270, D330	D2 D2	240, 300	M12: D360
Visit window in days	NA	N	IA	±2	±3	H	⊨ 3	±3	±3	:	±7	±7	=	±7	M12: ±7
IP (DE-109, Sham, Dummy) administration		x	b			Х	, b				X			X	
Time relative to IP administration		pre	post			pre	post			pre ^a	post ^a		pre	post	
Signed and dated informed consent	x ^c														
Inclusion/exclusion criteria	X	x													
Medical/surgical history, history of NIU-PS	x														
Demographics	X														
Physical examination and vital signs	x								x ^d						X
VFQ-25		x							x ^d						X
Serum pregnancy test ^e	x ^e														x ^e
Urine pregnancy test ^e		x ^e				x ^e				x e			x ^e		
Laboratory safety tests (hematology, chemistry, urinalysis) ^f	x ^f								x ^{d, f}						x ^f
Blood sample for pharmacogenomics ^g				x ^g											
Time relative to IP administration		pre	post			pre	post			pre ^a	post ^a		pre	post	
Randomization ^h		x ^h													

	Screening		Double-Masked Period Visits						Open-Label Period Visits						
	Screening (Within 30 days prior to D1; i.e., D -30 to D -1)	E (Bas	01 eline)	D14	M1	N N	12, 14	M3	М5	N	16 ^a	M7, M9, M11	N N	18, 110	M12/ Exit/ Early Termina- tion
Best-corrected visual acuity (ETDRS)	X	x		x	x	x		x	x	x		x	x		x
Slit-lamp biomicroscopy	X	x	x ⁱ	x	x	x	x ⁱ	x	x	x	x ⁱ	x	x	x ⁱ	x
Intraocular pressure	X	x	x ^j	x	x	x	x ^j	x	x	x	x ^j	x	x	x ^j	X
Indirect ophthalmoscopy	X	x	x ⁱ	x	X	x	x ⁱ	x	x	x	x ⁱ	x	x	x ⁱ	X
Optical Coherence Tomography		x		x	x	x		x	x	x		x	x		x
Fundus photography	X	x		x	x	x		x	x	x		x	x		X
Fluorescein angiography k		x						x	x						x
Systemic corticosteroid medication status	x ¹	x		x	x	x		x	x	x		x	x		X
Other prior or concomitant medications	X	x	x	x	x	x	x	x	x	x	x	x	x	x	x
Prednisolone acetate eye drops ^m			x ^m				x ^m				x ^m			x ^m	
Adverse events ⁿ	X	x	X	x	х	x	x	x	x	х	x	x	x	x	x

Table 1:Table of Activities (Continued)

IP = Investigational product; NA = not applicable; M=Month; D=Day; pre=prior to IP administration; post = after IP administration.

^a The double-masked period ends with the pre-dose evaluations at Month 6; the first open-label dose of DE-109 is at Month 6.

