4. TIME-RELATED TERMS

4.1. Baseline Visit

The *Baseline Visit* is the visit when a randomized subject receives the first administration of an investigational product (IP) (either an injection of DE-109 or a sham procedure).

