8.1.6. Rescue Therapy

Rescue therapy is defined as any treatment that would have a therapeutic effect on NIU-PS, other than intravitreal DE-109.

- Systemic corticosteroid therapy (except during the tapering window)
- New systemic treatment with an immunosuppressant agent
- Increase in dose of ongoing therapy with methotrexate, azathioprine, or mycophenolate mofetil (or an equivalent drug, e.g., mycophenolic acid)
- Anti-vascular endothelial growth factor therapy (anti-VEGF)
- New or increased dose/frequency of topical ocular corticosteroid to the study eye
- New or increased dose/frequency of topical ocular nonsteroidal anti-inflammatory agent to the study eye
- Ocular or periocular corticosteroid injection to the study eye

- Use of difluprednate ophthalmic emulsion eye drops in the study eye
- Vitrectomy in the study eye

Other protocol-allowed or specified medications that are not considered rescue therapy are listed as follows:

- Investigational product (DE-109, Sham, Dummy).
- Oral corticosteroids administered in accordance with the protocol-specified tapering schedule (refer to Protocol Section 6.5.3).
- Ongoing stable dose/frequency of corticosteroid eye drops is permitted (exception of difluprednate), non-steroidal anti-inflammatory eye drops, methotrexate, azathioprine, or mycophenolate mofetil are allowed by the protocol.
- The protocol-specified administration of prednisolone acetate eye drops following each IP administration.

Rescue therapies will be performed when worsening of uveitis in the study eye is observed satisfying one or more of the following three rescue criteria:

- 1. Worsening of uveitis in the study eye as indicated by at lease a 2-step increase in VH score (i.e., 0 to ≥2+, 0.5+ to ≥3+, 1+ to ≥3+, 1.5+ to ≥4+, or 2+ to ≥4+) as compared to the baseline (Day 1) VH score or the best achieved VH score post baseline.
- Severe deterioration of vision in the study eye due to worsening of uveitis that is indicated by at least doubling of the visual angle (BCVA loss of 3 or more lines [≥15 ETDRS letters]) as compared to baseline (Day 1) BCVA.
- 3. New or worsening retinal or choroidal uveitic lesion(s) in the study eye determined by clinical examination, as compared to baseline.

These three above criteria are generally referred to as protocol-specified rescue criteria.

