9.3. Intraocular Pressure

IOP and change from baseline in IOP will be summarized by analysis visit.

Change after injection in IOP will be summarized by injection visit. Subjects with any increase of ≥ 10 mmHg in IOP after injection will be listed.

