9.4.1. Lens

For phakic lens only, shift from baseline in cataract severity score will be summarized by analysis visit and shift after injection will be summarized by injection visit. Subjects with any worsening (increase) of 2 units or more from baseline in cataract severity will be listed. In addition, subjects with any cataract that affected grading of degree of inflammation will also be listed.

9.5. **Ophthalmoscopy**

For retina vessels, macula, fovea, periphery, and optic nerve, shift from baseline in status (Normal or Abnormal) will be summarized by analysis visit and shift after injection will be summarized by injection visit. Subjects with any change from Normal at baseline to Abnormal in status will be listed by ophthalmoscopic parameter.

For vitreous hemorrhage, retinal detachment, and retinal tear, shift from baseline in presence status (None or Present) will be summarized by analysis visit and shift after injection will be summarized by injection visit. Subjects with any change from None at baseline to Present in presence status will be listed by ophthalmoscopic parameter.

For cup/disc ratio, score and change-from-baseline score will be summarized by analysis visit. Change after injection in cup/disc ratio will be summarized by injection visit. Subjects with any worsening (increase) of 0.2 units or more from baseline in cup/disc ratio will be listed.

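### In former sham eyes, open-label safety changes are measured from Day 1, about 179 days before the first DE-109 injection, so the change and shift tables mix sham-period change with change on DE-109

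*SAP*

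**What the plan says.** SAP 8.1.2 states that for any measure the baseline score "is the last observed measurement prior to the first administration of the IP". The paragraph sits under the efficacy definitions, but SAP Section 9 offers no other baseline for safety.

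SAP 4.1 places the Baseline Visit at the "first administration of an investigational product (IP) (either an injection of DE-109 or a sham procedure". SAP 8.1.6 likewise lists Sham and Dummy beside DE-109 as investigational product. A sham eye's baseline is therefore fixed on Day 1.

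Note a to Table 1 in SAP 3.4 says that "the first open-label dose of DE-109 is at Month 6", and Protocol 8.1.10 sets that visit as "Allowable visit window: Day 180 ± 7 days".

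Safety data are then reported against this baseline at each nominal visit. SAP 9.3: "IOP and change from baseline in IOP will be summarized by analysis visit". For cup/disc ratio, SAP 9.5: "score and change-from-baseline score will be summarized by analysis visit". SAP 9.4, 9.4.1 and 9.5 do the same, as changes or shifts, for biomicroscopy, cataract severity and ophthalmoscopy. SAP 9.1.2 asks for change from baseline in every ocular safety measure; its Table 3 includes BCVA and central subfield thickness.

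SAP 6.7 creates an Open-Label Safety population for the open-label safety analyses, without a baseline of its own. SAP 4.4 starts the open-label treatment period at the first open-label injection.

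**The concern.** The open-label period is meant to show what happens to eyes on DE-109 440 µg. For an eye that had sham for six months, the status that matters is the one just before its first DE-109 injection. The SAP restarts the treatment clock for that eye at Month 6 but does not restart the reference value for its change scores.

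Much can happen to a sham eye before Month 6. Its uveitis may worsen or improve. It may receive rescue corticosteroid (Protocol 6.5.6), and it receives prednisolone acetate drops after every sham procedure (Protocol 6.5.5). Protocol 2.2 itself links systemic corticosteroids and corticosteroid implants to cataract and to glaucoma or raised IOP. Any such change is carried into the Month 7 to 12 figures. In the other direction, an eye that improved before Month 6 and then deteriorated after its first DE-109 injection can show little net change from Day 1.

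**Working it through.** **Inputs.** Nominal visit days come from Table 1 in SAP 3.4: Month 6 = Day 180, Months 7 to 12 = Days 210, 240, 270, 300, 330 and 360. SAP 4.3 makes the baseline visit Day 1. Arm sizes (80, 80, 40) are in SAP 3.2.

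**The plan's own figure.** The 80 per arm in SAP 3.3 reproduces. With 30% versus 12%, two-sided α = 0.05, 80% power and pooled variance under the null: n = [1.960 × √(2 × 0.21 × 0.79) + 0.842 × √(0.30 × 0.70 + 0.12 × 0.88)]² / 0.18² = 79.2, rounded up to 80. It is used here only for the share of subjects coming from sham: 80/200 = 40%.

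**Time before any DE-109.** Day 180 − Day 1 = 179 days. With the ±7-day window at Month 6 the range is 172 to 186 days.

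**Share of the change interval that precedes DE-109** = 179 / (visit day − 1):

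| Visit | Days from Day 1 | Days from Month 6 | Share before DE-109 |
|---|---|---|---|
| Month 7 | 209 | 30 | 86% |
| Month 8 | 239 | 60 | 75% |
| Month 9 | 269 | 90 | 67% |
| Month 10 | 299 | 120 | 60% |
| Month 11 | 329 | 150 | 54% |
| Month 12 | 359 | 180 | 50% |

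**What this could do to a threshold count (illustration; the means and SDs are assumed, not from the documents).** Take IOP change as normal with SD 4 mmHg in each six-month period, independent, and count rises of at least 10 mmHg. From Month 6 the SD is 4; from Day 1 it is √(4² + 4²) = 5.66. The chance is 1 − Φ((10 − mean change)/SD).

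| Mean change after DE-109 | From Month 6 | From Day 1, sham-period mean −3 | From Day 1, sham-period mean 0 | From Day 1, sham-period mean +3 |
|---|---|---|---|---|
| 0 mmHg | 0.6% | 1.1% | 3.9% | 10.8% |
| +3 mmHg | 4.0% | 3.9% | 10.8% | 24.0% |

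Under these assumptions the Day 1 count is mostly the larger, because it also carries the sham-period variation. It is marginally lower in one cell.

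**A single eye (illustration).** An eye that gains 12 letters by Month 6 and then loses 15 after its first DE-109 injection is recorded as +12 − 15 = −3 from Day 1, against −15 from Month 6.

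**Does another summary fill the gap?** Change after injection (SAP 8.1.4) compares readings at the same visit; IOP is read about 40 minutes after administration. BCVA and OCT have no post-administration assessment in Table 1. This summary therefore cannot give the change from pre-DE-109 status at a later visit.

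**The case against.** The strongest reply is that the main record of harm is already anchored correctly. SAP 4.4 starts the open-label period at the first open-label injection, and SAP 9.1.1 restricts open-label adverse event tabulations to events from the treatment start onward. A cataract with onset during the sham period is not counted as an open-label treatment-emergent event. This stands: a reader might infer that adverse event reporting is distorted too, and the documents do not support that. One limit remains. The IOP adverse event threshold (Table 1, note j) and the 15-letter vision criterion for events of special interest (SAP 9.1.1.5) also refer to Day 1, so the eye in the example would not meet the letter criterion, although the investigator-judgement route in the same section stays open.

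Second, the sham-period change is not hidden. Month 6 pre-dose is a scheduled visit, so change from Day 1 to Month 6 appears in the same tables, and observed values are also summarised for IOP and cup/disc ratio. This stands at group level. It does not give each eye's change or shift from its pre-DE-109 status, which cannot be recovered from two marginal tables.

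Third, safety is descriptive and untested, and SAP Section 5 allows unplanned additional analyses. That limits the consequence. But the SAP states a specific rule for these tables, and the better reference is already collected.

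**Conclusion.** The point holds for descriptive safety change and shift tables in former sham eyes at Months 7 to 12. Between 86% (Month 7) and 50% (Month 12) of each interval precedes any DE-109, on nominal visit days. About 40% of planned subjects are concerned, assuming equal retention to Month 6; the share of eyes also depends on how many subjects enrol both. Same-visit change after injection and all efficacy results are untouched, and open-label adverse event tabulations largely so.

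Three stronger readings go beyond the documents:

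- **A known direction.** A reader might infer that IOP and lens harm will be overstated and vision loss understated. Nothing in the documents shows how sham eyes move on these measures before Month 6, so the error can run either way.
- **A fixed size in a pooled table.** If 15% of sham eyes worsened by a lens grade before Month 6, pooling all arms would carry in 0.40 × 15% = 6 points; at 5% or 25% it would be 2 or 10 points. These rates are assumptions, and the SAP does not say whether open-label tables pool the former arms.
- **A failure of the one-year dosing evidence.** Former sham eyes can receive at most three DE-109 injections over six months, so they cannot supply one-year dosing data under any baseline.

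**What to change.** In SAP 8.1.2, with a cross-reference in Section 9:

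- Define an open-label baseline for eyes randomised to sham as the last value before the first open-label DE-109 injection. For the ocular measures this is normally the Month 6 pre-dose assessment.
- Use it for these eyes in all open-label safety change and shift tables.
- Present open-label tables by former randomised arm, so that six-month and twelve-month windows are not pooled. This also keeps apart the former dummy eyes, which move from an undisclosed fixed dose to 440 µg at Month 6.
- Keep the Day 1 version for whole-study summaries.

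The cost is one derived baseline, some wording and additional tables. Month 6 pre-dose BCVA, IOP, slit-lamp, ophthalmoscopy and OCT are already scheduled, so no new data are needed and no clinical rule changes.
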